5.6.2 Subject Withdrawal

Subject's authorized legal representative may voluntarily withdraw consent from the study or the investigator may terminate a subject's participation.

An investigator may terminate a study subject's participation in the study if:

- Any clinical adverse event (AE), laboratory abnormality, or other medical condition or situation occurs such that continued participation in the study would not be in the best interest of the subject.
- The subject meets an exclusion criterion (either newly developed or not previously recognized) that precludes further study participation.

Subject discontinuation due to an AE, or other medical condition, will be followed up by the clinical study site staff to insure appropriate care and to record any events that are related or unrelated to safety or effectiveness outcomes of this study and this will be reported to the DSMB.

5.6.3 Premature Termination or Suspension of Study

This study may be suspended or prematurely terminated if there is sufficient reasonable cause. See the list below. Written notification, documenting the reason for study suspension or termination, will be provided by the suspending or terminating party to the principal investigator, funding agency, the Investigational Device Exemption (IDE) sponsor and regulatory authorities. If the study is prematurely terminated or suspended, the principal investigator will promptly inform each of the IRBs and will provide the reason(s) for the termination or suspension. Circumstances that may warrant termination include, but are not limited to:

- Determination of unexpected, significant, or unacceptable risk to subjects resulting from the PCLC system or study design.
- Insufficient adherence to protocol requirements by the study team.
- Data that is not sufficiently complete and/or evaluable.

6 STUDY INTERVENTION

Study Product Description

The device used in the in study is a 731 Series ventilator whose software has been modified to include FiO₂ PCLC. In all other ways the device is identical to devices that are used routinely by civilian and military care providers. The 731 has an integrated pulse oximeter that provides the signal used by the PCLC algorithm to adjust the FiO₂ as required. In addition to the standard ventilator and pulse oximetry alarms, the modified code also has additional alarms that are related to PCLC, these are described in Appendix B. The data signal also includes all alarm and device condition information (power status, battery status, barometric pressure, ambient temperature, etc.).

6.1 Acquisition

Study product will be loaned to the study team by the sponsor and will include:

- Ventilator with modified software bearing appropriate investigation labeling
- Single-patient use breathing circuits
- Single-patient use pulse oximeter sensors
- AC/DC power supply
- Data acquisition computer with shielded USB interface cable
- Operating manual that covers both normal and PCLC operation and alarm features.

At the conclusion of the study or in the event the study is terminated prematurely, the ventilator and all durable accessories will be returned to the sponsor.

6.2 Formulation, Packaging, and Labeling

The ventilator will be labeled for investigational use only and will be under the control of the study team at each location. Consumables are not modified and are supplied in their standard packaging.

6.3 Product Storage and Stability

Product will be under the control of the study team at each location who will be responsible for configuring the system for use in the study. While the study will take place in an ICU setting the device is cleared for an extreme range of operating and storage environments and as such, no special storage requirements are necessary. Processing the device between patients will follow the procedures defined in the standard labeling which calls for single-use consumables to be discarded while the device is cleaned following the hospital's device cleaning procedures.

6.4 Accountability Procedures for the Study Product

Each study location will be provided with 2 systems, as described above. The systems will be under the control of the local study team. Consumables will be provided as needed. *At the conclusion of the study or in the event the study is terminated prematurely, the ventilator and all durable accessories will be returned to the sponsor.*

7 STUDY SCHEDULE

7.1 Screening

7.1.1 Visit 1: Screening/Enrollment

- Obtain and document consent from family member or legal representative on screening consent form.
- Review medical history to determine eligibility based on inclusion/exclusion criteria.
- Review medications history to determine eligibility based on inclusion/exclusion criteria.
- Perform medical examinations needed to determine eligibility.

7.1.2 Visit 2: Time 0 + 12 hours

- Administer the intervention that will be either manual control of FiO₂ or automated closed-loop-control of FiO₂ depending on the randomization assignment. Following administration of the intervention
- Assess physiological status
- Record adverse events as observed by investigator.
- Record results of physical examinations.
- Record any clinician changes in ventilator settings.
- Record any blood gas results from routine care
- Assess vital signs

7.1.3 Visit 3: Time 24 hours after the intervention

- Assess physiological status
- Record adverse events as observed by investigator.
- Record results of physical examinations.
- Assess vital signs

8. STUDY PROCEDURES /EVALUATIONS

8.1 Study Procedures/Evaluations

1. Medical history from medical records.
2. Physical examination (list the vital signs [including height and weight] and organ systems to be assessed. Address details in the MOP.); if appropriate, discuss what constitutes a targeted physical examination and at what visits it may occur.

8.2 Clinical Laboratory Evaluations

1. Baseline blood gas analyses, as ordered by the clinical team.
2. Arterial blood gases
3. Continuous transcutaneous oxygen saturation

9. ASSESSMENT OF SAFETY

This study involves a previously cleared continuous ventilator with an investigational component – the physiologic closed-loop controller. Reporting of certain events is mandatory because of the study population or study design characteristics; the study is conducted at multiple sites, and will require centralized safety oversight.

9.1 Specification of Safety Parameters

9.1.1 Primary Safety variable:

To assess the relative duration of time with SpO₂ <88% during the study period.

9.1.2 Secondary safety variables:

- Evaluation of missed diagnoses
- Rate of serious device-related AEs
- Rate of serious AEs not related to the device
- Rate of device-related AEs

9.2 Unanticipated Problems

We consider unanticipated problems involving risks to subjects or others to include, in general, any incident, experience, or outcome that meets the following criteria:

- Unexpected in terms of nature, severity, or frequency given (a) the research procedures that are described in the protocol-related documents, such as the IRB-approved research protocol and informed consent document; and (b) the characteristics of the subject population being studied;
- Related or possibly related to participation in the research (“possibly related” means there is a reasonable possibility that the incident, experience, or outcome may have been caused by the procedures involved in the research); and
- Suggests that the research places subjects or others at a greater risk of harm (including physical, psychological, economic, or social harm) than was previously known or recognized.

9.3 Adverse Events

An adverse event is any untoward or unfavorable medical occurrence in a human subject, including any abnormal sign (for example, abnormal physical exam or laboratory finding), symptom, or disease, temporally associated with the subject’s participation in the research, whether or not considered related to the subject’s participation in the research.

9.4 Serious Adverse Events

A serious adverse event (SAE) is one that meets one or more of the following criteria:

- Results in death
- Is life-threatening (places the subject at immediate risk of death from the event as it occurred)
- Results in inpatient hospitalization or prolongation of existing hospitalization
- Results in a persistent or significant disability or incapacity
- Results in a congenital anomaly or birth defect
- An important medical event that may not result in death, be life threatening, or require hospitalization may be considered an SAE when, based upon appropriate medical judgment, the event may jeopardize the subject and may require medical or surgical intervention to prevent one of the outcomes listed in this definition.

9.5 Frequency for Event Assessment and Follow-Up

Unanticipated problems will be recorded in the data collection system throughout the study.

The PI will record all reportable events with start dates occurring any time after the patient is randomized until 24 hours after the subject is removed from the study ventilator. At each study visit, the investigator will inquire about the occurrence of AE/SAEs since the last visit. Events will be followed for outcome information until resolution or stabilization.

9.6 Characteristics of an Adverse Event

9.6.1 Relationship to Study Intervention

To assess relationship of an event to study intervention, the following guidelines are used:

1. Related (Unlikely, Possibly, Related)
 - i. The event is known to occur with the study intervention.
 - ii. There is a temporal relationship between the intervention and event onset.
 - iii. The event abates when the intervention is discontinued.
 - iv. The event reappears upon a re-challenge with the intervention.
2. Not Related

- i. There is no temporal relationship between the intervention and event onset.
- ii. An alternate etiology has been established.

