4.2 Secondary Objectives

Four additional safety related question will be addressed:

1. The rate of serious adverse events related to the PCLC is not different than those attributed to the MC group
2. The rate of serious adverse events not related to the PCLC is not different than those attributed to the MC group
3. The number of missed diagnosis attributed to the PCLC is not different than those attributed to the MC group
4. The rate of device related adverse events related to the PCLC is not different than those attributed to the MC group.

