
For the analysis of secondary safety outcome, data point estimates will be reported with 95% confidence intervals followed by a Fisher's Exact Test at the 5% level of confidence. Specifically the percentage of subjects reporting at least one adverse event (i.e serious, any device related, etc.) will be calculated for each group and compared using Fisher's Exact Test. The relative risk of each adverse event with the corresponding two-sided 95% confidence interval will be presented.

Missing data: The primary analysis is an intent to treat analysis. In order to minimize the possibility of missing data, the total duration of monitoring will be extended for each subject as needed in order to collect at least 12 hours of evaluable data. As a sensitivity analysis, the primary outcome measure also will be calculated as the relative time the subject was on target compared to the total amount of time they were on manual or closed-loop control. Therefore each subject should have the outcome measurement. The amount of missing data is expected

to be low based on past experience with subject retention. However there is a very low probability that some subjects may die before completing 12 hours of monitoring on the device. In this case, the relative duration will be derived by using the total duration of time the subject was on target relative to the monitoring time until they died. If a subject does not have 12 hours of monitoring data on the device due to a reason other than death, we will conduct sensitivity analysis by assuming different scenarios. In a worst case scenario, the primary outcome will be computed as the total time in the target range divided by 720 minutes. In a best case scenario, the primary outcome will be computed as the total time in the target range divided by the total amount of time the subject was observed (i.e. <720 minutes). In the event of missing data on the primary safety and efficacy outcomes (except where the subject died), the reason for the missing values will be explored, and the pattern of missing values (e.g. missing at random, missing completely at random) will be evaluated. In addition, analyses excluding those subjects without 12 hours of monitoring will also be conducted as sensitivity analyses.

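### Section 9.6.1 files 'Unlikely' under Related, and no visible text sets a different cut for the device-related adverse event endpoints

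*Combined protocol and SAP*

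**What the plan says.** Section 9.6.1 sorts events by relationship to the study intervention under two headings. The first is "Related (Unlikely, Possibly, Related", so 'Unlikely' is one of three grades inside Related. The second is Not Related, with two criteria: an established alternative cause, and "There is no temporal relationship between the intervention and event onset".

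Section 9.1.2 lists the secondary safety variables. Three depend on relatedness: "Rate of serious device-related AEs", "Rate of serious AEs not related to the device" and "Rate of device-related AEs". Section 4.2 states the matching objectives as an absence of difference, with no margin; for example, "The rate of device related adverse events related to the PCLC is not different than those attributed to the MC group".

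Section 12.2 gives the analysis: the "percentage of subjects reporting at least one adverse event (i.e serious, any device related, etc.) will be calculated for each group". The arms are compared by Fisher's exact test at 5%, and relative risks are shown with two-sided 95% confidence intervals. It does not say which causality grades make an event device-related.

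Section 3.3 says that Appendix A also defines relatedness, including device and procedure relatedness. The text of that appendix is blacked out in the public copy.

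**The concern.** The only relatedness rule that can be read is the pair of headings in section 9.6.1. A programmer who follows it codes 'Unlikely' events as device-related and takes serious ones out of the not-related outcome. That reverses the investigator's judgement on each such event.

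The grade may well be used. Section 9.5 collects events from randomization until 24 hours after the subject leaves the study ventilator, in critically ill trauma and acute surgical patients. An event in that window with a temporal link and no proven alternative cause does not fit Not Related easily, and 'Unlikely' is a natural place for it.

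At stake is how the secondary safety comparison is read. The objectives are framed as no difference without a margin, so a non-significant Fisher test may be taken as support. A definition that mixes background events into the device-related count makes that result hard to interpret, whichever way it moves.

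**Working it through.** The plan states no event rate, effect size or power for these endpoints, so there is no figure to reproduce. The calculation shows only how the definition acts on the comparison.

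**From the documents:** 105 subjects per arm (section 5.2); percentage of subjects with at least one event, Fisher's exact test at 5%, relative risk (section 12.2). The sidedness of the test is not stated; two-sided is assumed.

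**Assumed, not from the documents:** the true device-related rates *p*, and the share *u* of subjects with an 'Unlikely' event, taken as independent of true device-related events.

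**Formula:** if 'Unlikely' counts as Related, the observed rate in an arm is 1 − (1 − *p*)(1 − *u*). Power is by full binomial enumeration of the exact test.

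**Case 1: equal 'Unlikely' shares, true rates 10% (PCLC) and 2% (MC).** For *u* = 10%, PCLC is 1 − 0.90 × 0.90 = 0.190 and MC is 1 − 0.98 × 0.90 = 0.118, so RR = 0.190/0.118 = 1.61.

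| *u* in both arms | PCLC | MC | RR | Risk difference | Power |
|---|---|---|---|---|---|
| 0 (kept out of Related) | 0.100 | 0.020 | 5.0 | 0.080 | 62% |
| 5% | 0.145 | 0.069 | 2.10 | 0.076 | 35% |
| 10% | 0.190 | 0.118 | 1.61 | 0.072 | 24% |
| 20% | 0.280 | 0.216 | 1.30 | 0.064 | 15% |
| 30% | 0.370 | 0.314 | 1.18 | 0.056 | 11% |

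The relative risk and the power fall sharply; the risk difference falls much less.

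**Case 2: unequal shares, no true effect (2% in both arms).**

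| *u*, PCLC vs MC | Observed rates | RR | Rejection |
|---|---|---|---|
| 0 vs 0 | 0.020 vs 0.020 | 1.0 | 0.5% |
| 10% vs 5% | 0.118 vs 0.069 | 1.71 | 17% |
| 10% vs 0 | 0.118 vs 0.020 | 5.9 | 78% |
| 20% vs 5% | 0.216 vs 0.069 | 3.13 | 84% |

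Here the error runs against PCLC.

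**Case 3: unequal shares the other way, true rates 10% and 2%.** With *u* = 0 in PCLC and 10% in MC, the observed rates are 0.100 and 0.118, so RR = 0.100/0.118 = 0.85. A real excess in the PCLC arm then appears as a slight deficit.

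Neither direction can be ruled out from the documents. The two strategies are evident at the bedside, only one arm has an active controller, and sections 7.1.2 and 9.6.1 describe no blinded assessor and no adjudication of relatedness.

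**The case against.** The strongest reply is that the operative definition may be out of sight. Section 3.3 points to Appendix A for device and procedure relatedness, while section 9.6.1 speaks of the study intervention and calls its lists guidelines. Sections 9.1.2 and 12.2 do not say that the analysis cuts between the two headings, and a cut at Possibly or Related would be compatible with keeping three grades. This stands as a limit: it cannot be said that the analysis will count 'Unlikely' events as device-related. It does not remove the point, because the visible heading assigns the grade to Related and would have to be reconciled with any different rule in Appendix A.

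A reader might infer that the scale necessarily pulls the comparison toward no difference and so toward false reassurance. The documents do not support that. It requires similar 'Unlikely' shares in both arms, and Cases 2 and 3 show what happens otherwise.

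A reader might also infer that the not-related outcome is emptied. It is not: events with an established alternative cause, or with no temporal link, still go to Not Related. The outcome is depleted by an unknown amount, which could be small. Section 3.3 reports very few safety events related to patient condition in the feasibility study.

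Counting doubtful events as related can also be defended as a cautious convention for safety reporting. It is less suitable as the only definition for a between-arm comparison. Two safeguards do not depend on the grade: section 12.2 compares subjects with any serious event, and section 9.6.4 has the DSMB review all SAEs whatever their cause.

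**Conclusion.** The point holds in limited form. The visible rule places 'Unlikely' under Related, and no visible text gives another cut for the three secondary outcomes that depend on relatedness. Followed as written, it dilutes the relative risk when grading is similar in the two arms and can bias it in either direction when grading differs.

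The size cannot be estimated from the documents. The figures above rest wholly on assumed rates and should not be read as this trial's power loss. The conclusion also assumes that Appendix A does not already set a different cut; if it does, the defect is an inconsistency between it and section 9.6.1. Both primary endpoints are measured as SpO2 time and are not touched. This is a minor point, cheap to settle before the data are analysed.

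**What to change.** Keep all the grades as collected. For the secondary endpoints, define device-related as Possibly or Related and group 'Unlikely' with Not Related. Tabulate 'Unlikely' events separately by arm, and add a sensitivity analysis that counts them as related. State the cut in section 12.2, and reconcile section 9.6.1 and the CRF coding with the relatedness definitions in Appendix A. Expedited reporting follows its own criteria in section 9.6.4 and need not change.

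The cost is about one line in each place and one extra table. The downside is that the main tabulation is less inclusive of doubtful events, which the sensitivity analysis covers. Fixing the cut in advance also avoids choosing the grouping after the results are known.

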9.6.2 Expectedness of SAEs

The Study PI will be responsible for determining whether an SAE is expected or unexpected. An adverse event will be considered unexpected if the nature, severity, or frequency of the event is not consistent with the risk information previously described for the intervention. All serious adverse events will be subsequently reported to the DSMB.

9.6.3 Severity of Event

The following scale will be used to grade adverse events:

1. Mild: no intervention required; no impact on activities of daily living (ADL)
2. Moderate: minimal, local, or noninvasive intervention indicated; moderate impact on ADL
3. Severe: significant symptoms requiring invasive intervention; subject seeks medical attention, needs major assistance with ADL

9.6.4 Reporting Procedures

SAE's require expedited reporting when meeting the following criteria:

- The incident is serious
- Unexpected given the subject's condition and use of mechanical ventilation
- Suspected adverse reaction to closed-loop control of FiO₂. This would include a determination by the PI that the event is **not** related to consequences of the underlying disease or condition under study or events common in the study population.

These events are required to be reported to the FDA within 7 calendar days of the sponsor's initial receipt of the information if characterized as fatal or life-threatening. Non-fatal or non-life threatening events must be reported no later than 15 calendar days after the sponsor determines that the serious suspected adverse reaction (SSAR) or other information qualifies for reporting.

All SAEs are to be reported to the IRB and the DSMB as per policy.

The Data Safety Monitoring Board (DSMB) will be required to review all SAEs periodically regardless of causality.

10. STUDY OVERSIGHT

10.1 Data Safety Monitoring Board

An independent Data and Safety Monitoring Board (DSMB) composed of members with expertise in clinical medicine, mechanical ventilation, anesthesia, and biostatistics will provide oversight of safety events. The DSMB will meet after approximately 25%, 50%, and 75% of the study is enrolled, but not less than once per year. If safety concerns arise, more frequent meetings may be held. The DSMB will operate under the rules of the approved charter.

- The DSMB will contact Zoll to assure there is prompt identification of any adverse event(s) that could affect either human subject protection and/or clinical study data quality. This monitoring will include both on-site and off-site file review of the communal data depository which will have all of the IDE data, forms etc.
- Adverse events are defined in Appendix of the Protocol.
- Adverse events and safety data will also be reviewed by the study medical monitor who will have authority to terminate the study at any time due to safety concerns.
- ZOLL is responsible for stopping the trial if there is a risk to either human subject protection and/or clinical study data quality and reporting the decision to the FDA.

10.2 Training

The procedures for the physiologic closed-loop ventilation on the 731 Series ventilators are familiar to the University of Cincinnati Medical Center (UC). The staff has been trained and is experienced with the 731 Series ventilator as the device is currently used at UC for care and transport of patients. Training for the other clinical sites will be performed by staff from UC, based on their expertise, training and a Modified Operation Manual. Training will detail: study design, contraindications of use, using the closed-loop system, new alarms associated with the closed-loop functionality, interpreting the closed loop symbols on the user interface, documentation requirements (case report form) and adverse event reporting.

